9.2.4. Inclusion Criteria for the PM/CRT-P Cohort

Subjects enrolled in the PM/CRT-P cohort must also meet all of the following inclusion criteria (in addition to the General Inclusion Criteria):

Table 9.2-4: Inclusion Criteria for the PM/CRT-P Cohort

1. Subjects with a PM or CRT-P implanted during last 45 days prior enrollment (only BSC PG devices)
2. Subjects who are estimated to require right ventricle (RV) pacing >40%
3. PM subjects with LVEF \leq 50%
4. Paced or intrinsic QRS >90 ms, and any determined NYHA Class (symptoms of HF) or any previous HF admission (HF admission comprises the following conditions: admission to hospital because of HF and/or IV therapy for HF and/or upgrade of the PM/CRT-P)
5. Subjects' devices are currently intended to be followed on Latitude system.

Abbreviations: BSC = Boston Scientific; CRT-P = cardiac resynchronization therapy-pacemaker; HF = heart failure; LVEF = left ventricular ejection fraction; NYHA = New York Heart Association; PM = pacemaker; RV = right ventricle

9.2.5. Inclusion Criteria for the Non-device Cohort (ESC Guideline 2016 Indicated but not implanted)

Subjects enrolled in the Non-device cohort (ESC Guideline 2016 indicated but not implanted) must also meet all of the following inclusion criteria (in addition to the General Inclusion Criteria):

Table 9.2-5: Inclusion Criteria for the Non-device Cohort (ESC Guideline 2016 Indicated but not implanted)

- Subjects with symptomatic HF (NYHA Class II-III), and an LVEF $\leq 35\%$
- Subjects are on OMT ≥ 3 months
- Subjects are expected to survive substantially longer than 1 year with good functional status
- Subjects have ischemic heart disease or DCM (dilated cardiomyopathy)

OR

- LBBB QRS (≥ 130 ms) morphology and with LVEF $\leq 35\%$ despite OMT or
- QRS duration ≥ 150 ms and non-LBBB QRS morphology and with LVEF $\leq 35\%$ despite OMT

AND

1. No present or past implant device ICD, CRT-D, PM, or CRT-P
2. 2 to 5 risk factors out of the following:
 - LVEF $\leq 35\%$
 - NYHA Class III or IV
 - LBBB with QRS > 130 ms or any QRS > 150 ms
 - Renal dysfunction (chronically BUN > 26 mg/dL / > 9.28 mmol/L)
 - Diabetes type I and II
 - Chronic atrial fibrillation (permanent or persistent according to ESC Guideline 2016¹¹)
 - Prior MI
 - Age > 70 years
 - Smoking today or during last 5 years.

Abbreviations: BSC = Boston Scientific; BUN = blood urea nitrogen; CRT-D = cardiac resynchronization therapy-defibrillator; ESC = European Society of Cardiology; HF = heart failure; LBBB = left bundle branch block; LVEF = left ventricular ejection fraction; MI = myocardial infarction; NYHA = New York Heart Association; OMT = optimal medical therapy; PM = pacemaker

9.3. *Exclusion Criteria*

All exclusion criteria apply only at the time of enrolment into the study.

If a subject's medical conditions change after inclusion into the study so that one or several of the general exclusion criteria and exclusion criteria of the pertinent cohort are no longer met, the subject remains in the study.

If it turns out after enrolment into the study that one or several of the general exclusion criteria and exclusion criteria of the pertinent cohort were violated at the time of enrolment into the study, the study has to be ended in this subject.

9.3.1. General Exclusion Criteria

Subjects who meet any one of the following criteria (Table 9.3-1) are not allowed to be included in this clinical study. The exclusion criteria apply only at the time of enrolment into the study.

Table 9.3-1: General Exclusion Criteria

1. Subject is enrolled in any other concurrent study without prior written approval from BSC, with the exception of local mandatory governmental registries and observational studies/registries that are not in conflict and do not affect the following:
 - Schedule of procedures for the HINODE Study (i.e. should not cause additional or missed visits)
 - HINODE Study outcome
 - Conduct of the HINODE Study per Good Clinical Practice (GCP)/ International Standard Organization (ISO) 14155:2011/local regulations as applicable
2. Device implant revision is scheduled due to unstable result of an implant <45 days prior enrolment
3. Subjects with more than 5 of the following risk factors: LVEF \leq 35%, NYHA Class III or IV, LBBB with QRS 130 ms or QRS $>$ 150 ms, renal dysfunction (chronically BUN $>$ 26 mg/dL / $>$ 9.28 mmol/L), diabetes type I and II, chronic atrial fibrillation (permanent or persistent according to ESC Guideline 2016¹¹), prior MI, age $>$ 70 years, smoking today or during last 5 years
4. Subjects with chronic renal disease with chronic BUN \geq 50mg/dL or creatinine \geq 2.5 mg/dL
5. Subjects with coronary artery bypass graft (CABG) surgery or percutaneous coronary intervention (PCI) within the past three calendar months prior to enrollment
6. Subjects with enzyme-positive myocardial infarction within the past three calendar months prior to enrollment
7. Subjects who are expected to survive for <1 year with good functional status
8. Subject's physician does not allow participation
9. Subject is not willing and capable of participating in all testing or visits associated with this clinical study at an approved clinical study center and at the intervals defined by this CIP
10. Unwilling to sign the consent for participation
11. Women of childbearing potential who are or might be pregnant at the time of study enrolment
12. ICD and CRT-D cohorts: implanted with a non-BSC device system. PM/CRT-P cohorts: implanted with a non-BSC PG device.

Abbreviations: BSC = Boston Scientific; BUN = blood urea nitrogen; CIP = Clinical Investigation Plan; ESC = European Society of Cardiology; GCP = Good Clinical Practice; HF = heart failure; ISO = International Standard Organization; LBBB = left bundle branch block; LVEF = left ventricular ejection fraction; MI = myocardial infarction; NYHA = New York Heart Association

9.3.2. Exclusion Criteria for the ICD and CRT-D Cohorts

Subjects who meet any one of the following criteria (Table 9.3-2) will be excluded from the ICD and CRT-D cohorts of the study.

Table 9.3-2: Exclusion Criteria for the ICD and CRT-D Cohorts

1. CRT implanted in subjects with a QRS duration <130 ms
2. Subjects who have recovered from a ventricular arrhythmia causing hemodynamic instability
3. Subjects with NYHA Class IV (for ICD subjects)
4. Existing or previously implanted ICD, CRT-P, CRT-D, or pacemaker device system.

Abbreviations: BSC = Boston Scientific; CRT = cardiac resynchronization therapy, CRT-D = cardiac resynchronization therapy-defibrillator; ICD = implantable cardioverter-defibrillator

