Study Objectives	
The purpose of this cohort therapy study is to collect clinical event and outcome data in a study population with a majority of Japanese subjects on sudden cardiac death (SCD), heart failure (HF) events, and appropriately treated ventricular adverse events in predefined subject cohorts. These event rates will be compared with available data mainly from Europe and the United States. It is the intention to add evidence in treatment with implanted Implantable cardioverter-defibrillator (ICD) and treatment with cardiac resynchronization therapy-defibrillator (CRT-D) devices.
 
Selected Subject Cohorts:
 
1. Selected subject cohort with criteria for SCD (without spontaneous prior ventricular sustained arrhythmia) and de novo ICD device treatment.2. Selected subject cohort with criteria for SCD and widely accepted standard cardiac resynchronization therapy (CRT) indication who received a de novo CRT-D device treatment.3. Selected subject cohort who are clinically expected to require >40% right ventricular pacing with a left ventricular ejection fraction (LVEF) ≤50%, any determined New York Heart Association (NYHA) Class, and receiving pacemaker (PM) or CRT-pacemaker (CRT-P) therapy despite previous device history (de novo, box changes, system revisions or upgrades).4. Selected subject cohort with criteria for SCD fulfilling European Society of Cardiology (ESC) ICD or CRT-D therapy guidelines (2016) with an LVEF ≤35%, having 2 to 5 predefined SCD risk factors but do not have or had have a cardiac implanted defibrillator, CRT-D, PM, or CRT-P.
Test Device	
Implanted subjects will receive one of 4 types of Boston Scientific (BSC) devices prior to enrolment in the study:
 
1. ICD (only magnetic resonance imaging [MRI] conditionally safe systems) + Latitude

Heart Failure Indication and Sudden Cardiac Death Prevention Trial Japan
HINODE

Test Device (continued)	
2. CRT-D (IS4 connector only, MRI conditionally safe systems) + Latitude
 
3. PM + Latitude or CRT-P + Latitude

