1. Selected subject cohort with criteria for SCD (without spontaneous prior ventricular sustained arrhythmia) and de novo implanted Defibrillator device treatment (ICD).
2. Selected subject cohort with criteria for SCD and widely accepted standard CRT indication who received a de novo implanted CRT-D device treatment.
3. Selected subject cohort who are clinically expected to require >40% right ventricular pacing with an LVEF $\leq 50\%$, any determined New York Heart Association (NYHA) Class, and receiving PM or CRT-P therapy despite previous device history (de novo, box changes, system revisions or upgrades).
4. Selected subject cohort with criteria for SCD fulfilling European Society of Cardiology (ESC) ICD or CRT-D therapy guidelines (2016) with an LVEF $\leq 35\%$, having 2 to 5 predefined risk factors but do not have or have had a cardiac implanted device ICD, CRT-D, PM, or CRT-P.

Figure 3.2-1: HINODE Sample Size

7. Study Endpoints

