9.2.2. Inclusion Criteria for the ICD Cohort

Subjects enrolled in the ICD group must also meet all of the following inclusion criteria (in addition to the General Inclusion Criteria):

Table 9.2-2: Inclusion Criteria for the ICD Cohort

1. De novo ICD system implanted successfully 45 days prior enrollment in subjects with symptomatic HF (NYHA Class II–III), and an LVEF $\leq 35\%$
2. Subjects are on OMT ≥ 3 months
3. Provided that the subjects are expected to survive substantially longer than one year with good functional status
4. Subjects have ischemic heart disease or DCM (dilated cardiomyopathy)
5. Subject was implanted with a BSC MRI Conditional System
6. Subjects have 2 to 5 risk factors out of the following prior device implant:
 - LVEF $\leq 35\%$
 - NYHA Class III or IV
 - Left bundle branch block (LBBB) with QRS >130 ms or any QRS >150 ms
 - Renal dysfunction (blood urea nitrogen chronically [BUN] >26 mg/dL)
 - Diabetes type I and II
 - Chronic atrial fibrillation (permanent or persistent according to ESC Guideline 2016¹¹)
 - Prior MI
 - Age >70 years
 - Smoking today or during last 5 years
7. Clinical subject conditions allow programming of defibrillation therapy according to the principals of the MADIT RIT study programming
8. Subjects' devices are currently intended to be followed on Latitude system

Abbreviations: BSC = Boston Scientific; BUN = blood urea nitrogen; ESC = European Society of Cardiology; HF = heart failure; ICD = implantable cardioverter-defibrillator; LBBB = left bundle branch block; LVEF = left ventricular ejection fraction; MI = myocardial infarction; MRI = magnetic resonance imaging; NYHA = New York Heart Association; OMT = optimal medical therapy

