10.1. Point of Enrolment

Subjects will only be enrolled in this registry study if they meet all eligibility criteria and provide written informed consent. If a subject is found not to meet all applicable eligibility criteria, the subject will be withdrawn from the study; any points of ineligibility must be clearly documented in the enrolment/screening log. These subjects will be considered

consent ineligible as discussed in Section 10.3, and will not count towards the enrolment ceiling. Any subject that signs consent and meets all inclusion criteria and does not meet any Exclusion Criteria will be enrolled in the study. Any reportable events, as defined in Section 20 of this CIP, must be collected after written informed consent is obtained.

Subjects enrolled under protocol version C deviating from eligibility criteria of protocol version D will be withdrawn from the study. Other subjects previously not meeting eligibility criteria of protocol version C, but now meeting eligibility criteria of protocol version D, will be accepted under protocol version D and no protocol deviation will need to be documented in the eCRF.

10.2. *Withdrawal*

All subjects enrolled in this registry study (including those withdrawn from the clinical study or lost to follow-up) shall be accounted for and documented. If a subject withdraws from the study, the reason(s) shall be reported. If such withdrawal is due to problems related to investigational device safety or performance, the investigator shall ask for the subject's permission to follow his/her status/condition outside of the clinical study.

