- **Associated diseases/risk factors:** previous MI; previous hospitalization for HF; hypertension; diabetes type I and II; renal disease (BUN); chronic pulmonary disease; smoking in the last 5 years, peripheral artery disease; other known malignancies (tumor, lymphoma or leukemia); other chronic diseases.
- **Additional rhythm disease:** information will be collected on additional relevant rhythm diseases: AV block; sinus node dysfunction; paroxysmal, chronic, persistent atrial fibrillation; chronotropic incompetence.
- **Other subject history:** previous stroke; shock; previous ablation (AV node, atrial fibrillation or atrial flutter).
- **LVEF:** measured or estimated within the last 12 months and documented in the subject's medical file: fully preserved ($\geq 50\%$); partially preserved (40%-49%); reduced (<40%).
- **QRS:** intrinsic
- **Current/concomitant cardiac medication:** documentation of the following current/concomitant medication classes being administered: Angiotensin Converting Enzyme (ACE)-inhibitor/Angiotensin II (ATII) receptor antagonist; antiarrhythmic; anticoagulant; antiplatelet; Aldosterone-antagonist; beta-blocker; Digitalis; diuretics; statins; calcium antagonists.

Documentation of implanted devices

- **ICD, CRT-D, PM/CRT-P, etc. data:** Implant date, number of days implanted, model, serial number
- **Pacing lead data:** cardiac chamber (atrial and ventricular), number of days implanted and lead model (serial number) and manufacturer

Some subjects received a device system for the first time whereas others received a replacement procedure of existing systems (usually pulse generator due to battery depletion but may also include lead extractions due to lead failure or other reasons for system component replacement). Data (implant date, number of years implanted, model and manufacturer) for previous device systems will also be collected.

Defibrillator therapy for all ICD and CRT-D devices in the protocol must be programmed according to the specifications provided in Table 11.4-1, Table 11.4-2 and Table 11.4-3, respectively.

Any deviation from protocol requirements for medical reasons will need to be documented as an adverse event and as a deviation from the protocol. The programming is considered non-invasive; specifications are provided to ensure that the devices are operated per BSC IFU. Any programming not per the specifications below will be considered a CIP violation.

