12.2. General Statistical Methods

12.2.1. Analysis Sets

All subjects actively enrolled in the study (i.e. who meet all eligibility criteria at the time of enrolment into the study and who have given written informed consent) will be included in the primary endpoints analyses.

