26.2. Definitions

Terms are defined in Table 26.2-1.

Table 26.2-1: Definitions

Term	Definition
Cardiac Perforation	Penetration of the lead tip through the myocardium to the pericardium or beyond (including micro-perforation), either clinically suspected by chest x-ray, fluoroscopy or, intra-cardiac electrogram and/or confirmed by echocardiogram, CT or visually at operation.
Cardiac Tamponade	Also known as pericardial tamponade is an acute type of pericardial effusion in which hemodynamic compromise results and urgent intervention is required. This will be considered a SADE.
Complication	An adverse event that resulted in: death, serious injury, a correction using invasive intervention, or permanent loss of device functions.
Conductor Fracture/Lead Fracture	A mechanical break/disruption within the lead conductor (includes connectors, coils and/or electrodes) observed visually, electrically or radiographically.
Device-related Complication	A complication (an AE that resulted in death, serious injury, a correction using invasive intervention, or permanent loss of device functions) assessed as related to the device.
Elevated Pacing Thresholds	At implant, pacing thresholds for the permanently programmed electrode that are greater than 3.0 volts and at follow-up pacing thresholds for the permanently programmed electrode that are either: (1) An observed increase of 2-fold over the first chronic threshold; or (2) An observed threshold greater than 3.5 volts. Please note that these elevations in pacing threshold values may be physiologic, pathologic or device-related.
Extra-cardiac Stimulation (e.g., phrenic, diaphragm)	Clinical observation of inadvertent muscle/nerve stimulation other than cardiac muscle.
Hematoma	If a hematoma requires invasive intervention to evacuate the hematoma, it will be considered a SAE.
Hemodynamic instability	A state requiring pharmacological or mechanical support to maintain a normal blood pressure or adequate cardiac output.
High Pacing Impedance	Pacing impedance is considered abnormal based on lead model and measurement range of the device.
High Shock Impedance	Shock impedance is considered abnormal based on lead model and measurement range of the device.
High Shock Impedance when attempting to deliver a shock	High shock impedance is considered abnormal based on lead model and measurement range of the device when attempting to deliver a shock.

Table 26.2-1: Definitions

Term	Definition

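### The ICD objective rules out any prior spontaneous sustained ventricular arrhythmia, but the eligibility criteria exclude only arrhythmia with hemodynamic instability, so patients with tolerated sustained VT are eligible and no dedicated field flags them

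*Combined protocol and SAP*

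**What the plan says.** The first cohort in the synopsis is "Selected subject cohort with criteria for SCD (without spontaneous prior ventricular sustained arrhythmia) and de novo ICD device treatment". Section 6 repeats the qualifier. It is attached to the ICD cohort only; the CRT-D cohort description has no equivalent.

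Table 9.3-2 item 2, which applies to ICD and CRT-D together, excludes "Subjects who have recovered from a ventricular arrhythmia causing hemodynamic instability". Table 9.3-3 item 1 applies the same wording to the Non-device cohort. Section 26.2 defines hemodynamic instability as "A state requiring pharmacological or mechanical support to maintain a normal blood pressure or adequate cardiac output".

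Entry depends on the listed criteria. Section 10.1 states: "Any subject that signs consent and meets all inclusion criteria and does not meet any Exclusion Criteria will be enrolled in the study". Section 12.2.1 puts into the primary analyses "All subjects actively enrolled in the study (i.e. who meet all eligibility criteria at the time of enrolment into the study" and have consented; Section 12.1.1.2 says the same for the ICD endpoint.

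On rhythm history at enrolment, Section 11.4 says "information will be collected on additional relevant rhythm diseases: AV block; sinus node dysfunction; paroxysmal, chronic, persistent atrial fibrillation; chronotropic incompetence". Ventricular arrhythmia is not on that list.

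**The concern.** The objective and the exclusion draw the line in different places. The objective turns on whether a sustained ventricular arrhythmia ever occurred spontaneously; the exclusion turns on whether it was hemodynamically tolerated. Patients between the two lines have already had an event of the kind the primary endpoint counts, namely a first appropriately treated ventricular arrhythmia or associated life-threatening symptoms.

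Two things are at stake. The first is description: an ICD rate that includes patients with this history is not the rate in the stated cohort. The second is comparison. The study sets its rates against US and European data, and compares the defibrillator cohort with the Non-device cohort. If some ICD subjects carry this history unrecorded, a difference in either comparison could partly reflect case mix. The seven-factor propensity score in Section 12.3 contains no arrhythmia-history term and could not adjust for it.

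**Working it through.** **Step 1. Does any other criterion close the gap?**

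| Source | Bearing on prior tolerated sustained VT |
|---|---|
| Synopsis and Section 6, cohort 1 | Rules it out |
| Table 9.2-1, general inclusion | Silent |
| Table 9.2-2, ICD inclusion | Silent; item 7 concerns programming feasibility |
| Table 9.3-1, general exclusion | Silent |
| Table 9.3-2 item 2 with Section 26.2 | Excludes only if support was needed |
| Section 10.1 | Listed criteria decide enrolment |
| Sections 12.1.1.2 and 12.2.1 | All actively enrolled subjects are analysed |

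No listed criterion closes it.

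**Step 2. Is the history recorded elsewhere?** It is not in the Section 11.4 rhythm list, the nine-item risk-factor list in the same section, or the baseline variables in Section 12.3.6. Section 10.1 collects reportable events only after consent, so an arrhythmia before implant is not captured as an event.

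**Step 3. Reproduce the plan's own ICD figure.** Inputs from the synopsis and Table 12.1-1: goal 85%, expected event-free rate 95%, one-sided alpha 0.025, power 90%, attrition 20%, exact binomial.

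- With n = 93, the smallest rejecting count is 86 event-free: P(X ≥ 86 | 0.85) = 0.0235.
- Power: P(X ≥ 86 | 0.95) = 0.906. At n = 92 power is 0.823, and 93 is the smallest n that reaches 90%.
- 93 / 0.80 = 116.25, rounded up to 117.

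Both stated figures, 93 and 117, reproduce.

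**Step 4. Illustrate the sensitivity.** Let f be the share of ICD subjects with prior tolerated sustained VT and r their 12-month event rate. Neither is in the documents; both are assumed. All other subjects keep the planned 5%.

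Event-free rate = 1 − [(1 − f) × 0.05 + f × r]

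The ICD range is 117 to 270 enrolled. After 20% attrition the maximum leaves 270 × 0.80 = 216 evaluable, where success needs 195.

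| f | r | Event-free rate | Power, n = 93 | Power, n = 216 |
|---|---|---|---|---|
| 0 | – | 0.9500 | 0.91 | 0.999 |
| 2% | 20% | 0.9470 | 0.88 | 0.997 |
| 5% | 20% | 1 − (0.0475 + 0.010) = 0.9425 | 0.83 | 0.99 |
| 10% | 30% | 1 − (0.0450 + 0.030) = 0.9250 | 0.60 | 0.91 |
| 15% | 40% | 1 − (0.0425 + 0.060) = 0.8975 | 0.25 | 0.45 |

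**Step 5. Dilution in the pooled analysis.** The synopsis makes ICD and CRT-D combined the primary analysis and the separate cohorts descriptive. At the minimum evaluable numbers (93 ICD, 76 CRT-D), ICD subjects are 93 / 169 = 55% of the pool. Falls in the ICD event-free rate of 0.75, 2.5 and 5.25 percentage points (the last three rows) become about 0.4, 1.4 and 2.9 points. This counts ICD subjects only. The goals are stated by cohort (85% and 87%), with none for the pool, so pooled power is not computed here.

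**The case against.** The strongest reply is that the documents do not show this matters in numbers. That largely stands.

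- **Eligible is not enrolled.** A reader might infer that such patients are in the cohort. The documents show only that they could be, and item 7 ("Clinical subject conditions allow programming of defibrillation therapy according to the principals of the MADIT RIT study programming") may screen some out in practice.
- **Power.** A reader might infer that the trial becomes underpowered. The low figures depend on assumed shares and rates, on ICD alone, and on the minimum of 93 evaluable. At 216 only the most extreme of these scenarios falls below 0.90. The planned method is also Kaplan-Meier with a log-log bound, not an exact binomial.
- **Treated rate.** Neither Table 11.4-1 nor Table 11.4-2 delivers therapy below 170 bpm, and Table 11.4-1 only monitors between 170 and 200 bpm. Some recurrences would go untreated, so 20–40% may be too high.
- **Reference rate.** A reader might infer that the 5% figure was set for patients without this history. The plan says only that it rests on the MADIT RIT study, whose history criteria it does not give. Confounding of the comparison is possible, not shown.
- **Identification.** That these patients could never be found later is too strong. Antiarrhythmic use and some ablation history are collected, and hospital and implant records are retained. What holds is that no dedicated field is listed.
- **Direction.** If these subjects have more events than planned, the 85% goal becomes harder to meet. False success is not inflated.

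None of this reconciles the objective with the exclusion. A larger sample restores power but does not change which population is described.

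**Conclusion.** The mismatch is real and confined to the ICD cohort. As written, the plan can enrol and analyse subjects whom its own objective excludes, with no dedicated field to separate them. It should be fixed, but it does not invalidate the design.

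Its size cannot be derived from the documents. Under assumed shares of 5–15% and treated rates of 20–40%, ICD-only exact-binomial power falls from 0.91 to between 0.83 and 0.25 at 93 evaluable; at 216 it lies between 0.99 and 0.45. The effect is smaller in the pooled analysis. The firmer consequence is interpretive: the ICD rate may not describe the stated population or compare cleanly with the reference data.

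A reader might also infer that CRT-D patients with this history are wrongly admitted. The documents do not support that, since no objective excludes them.

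**What to change.** 1. Reconcile the ICD cohort description (synopsis and Section 6) with the arrhythmia exclusion (synopsis and Table 9.3-2 item 2). Either text could be amended; the choice is the sponsor's. Table 9.3-2 is shared, so a change made for ICD should not pass to CRT-D by default.
2. Check the result against the identical exclusion in Table 9.3-3, because the defibrillator and Non-device cohorts are compared in a secondary endpoint and in the propensity-matched analysis.
3. Add one yes/no eCRF item on prior spontaneous sustained VT or VF (ventricular fibrillation) for the ICD, CRT-D and Non-device cohorts, completed from source records for subjects already enrolled.
4. Report the ICD and pooled primary rates, and the defibrillator versus Non-device comparison, with and without flagged subjects.
5. State how already enrolled subjects are handled. Under Section 10.1, subjects enrolled under version C who deviated from version D criteria were withdrawn; a further change to eligibility needs its own explicit rule.

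The cost is a protocol amendment with a transition rule, one data item with retrospective completion, and one sensitivity analysis. If the exclusion is the text amended, a few ICD candidates may be lost.
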